From historical data on pregnancies at ChristianaCare Health System, we estimated a historical preterm birth rate of 9.1%. The sample size estimation is based on simulations of co-primary outcomes based on a simulated distribution of gestational age with a singleton preterm birth rate of 9.1%, and an effect of intervention based on literature data²⁶⁻²⁸, with α -level spending of 0.05 shared between co-primaries using Holm's method.

Given shut-down of the study due to the SARS-CoV-2 pandemic, the sample size for the study is estimated to be approximately 1,453 subjects in the prospective arm, and approximately 10,000 in the historical control group. In the primary and alternative analyses, more than 10,000 subjects may meet the eligibility criteria for the historical control group and have the required data, and if so, they will be included in the study.

Power and sample size for this study are affected by factors including the proportion of prospective subjects receiving PreTRM® risk scores at or above the threshold of 16% risk (the study Screen Positive Rate (SPR)), the proportion of higher-risk subjects complying with interventions (compliance), and the rate at which subjects and their neonates remain in the study (retention). For the purpose of power and sample size estimation and based on study monitoring, we estimate that 34% of subjects in the pre-pandemic portion of the prospective arm had PreTRM® risk scores at or above the threshold of 16% risk (the SPR).

Power and sample size are also affected by the study population's baseline level of risk of adverse neonatal outcomes related to prematurity, the sensitivity of testing in identifying at-risk pregnancies, retention of subjects in the study and the efficacy of the interventions as implemented in the study. Literature²⁶⁻²⁸ indicates that the effect of treatment is not constant across different values of GAB. Thus, there is no single value of the effect size in terms of proportion of subjects with NMI less than 3, or mean length of stay. Rather, the effect size is larger for subjects with earlier GAB, while the effect size is reduced for subjects with later GAB.

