The use of antenatal corticosteroids will be assessed in relation to primary, secondary and exploratory endpoints, and will be compared between the preterm prevention arm and historical controls, and between higher risk and not higher risk subjects in the preterm prevention arm. Optimal timing of dosing of antenatal corticosteroids is herein defined as 2 to 7 days (inclusive) prior to delivery at less than 37 weeks of gestation. Use of antenatal corticosteroids will be expressed as a binary variable: were steroids given in the optimal interval between dose and delivery? Significance of interaction between optimally timed use of antenatal corticosteroids and the specified treatment groups will be assessed in regression as an interaction term: (binary variable) * group. This analysis will be performed without adjustment, adjusted for covariates as specified for the primary analysis, and adjusted via propensity scoring as specified for the alternative analysis. Missing values will be addressed as previously specified for exploratory analyses: by omission of subjects with missing values and by replicating the analysis with multiple imputation of missing values.

Primary, secondary and exploratory endpoints will be assessed in the prospective portion of the mITT population as dependent responses to nonrandom quantitative assignment of treatment⁴². The independent quantitative assignment variable will be the PreTRM® risk score. The functional relationship between endpoints and the risk score will be estimated for the prospective arm. A discontinuity at the intervention threshold in the relationship between outcome and risk score observed in the prospective arm will demonstrate intervention effect, measured as the estimated magnitude of the discontinuity and re-assessed as the estimated risk-score dependent difference between compliant completers and non-intervention completers. As this analysis involves only prospective subjects, it is independent of any selection biases or epoch effects present in comparisons of the prospective arm relative to historical controls. To adjust for any biases present within the

prospective arm, the analysis will be performed without adjustment, adjusted for covariates as specified for the primary analysis, and adjusted via propensity scoring as specified for the alternative analysis.

The primary, secondary and exploratory endpoints will be applied to comparisons within the mITT population.

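### The antenatal steroid variable can be yes only for births before 37 weeks, but its regression is not limited to those births, so for all-birth endpoints it mainly marks preterm birth

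*SAP*

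**What the plan says.** The antenatal corticosteroid paragraph of SAP section 5.7 makes five choices.

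- **Definition.** Optimal timing is "herein defined as 2 to 7 days (inclusive) prior to delivery at less than 37 weeks of gestation".
- **Coding.** "Use of antenatal corticosteroids will be expressed as a binary variable: were steroids given in the optimal interval between dose and delivery". This is one yes/no variable; steroids given outside the interval and steroids not given are not separated.
- **Endpoints.** Steroid use "will be assessed in relation to primary, secondary and exploratory endpoints". No sentence limits this to preterm births.
- **Model.** The modification question is "assessed in regression as an interaction term: (binary variable) * group". The groups are prospective versus historical, and also "between higher risk and not higher risk subjects in the preterm prevention arm".
- **Adjustment.** None, or "adjusted for covariates as specified for the primary analysis", or the propensity score. Neither candidate list in section 5.3 contains gestational age at birth or preterm status.

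The same paragraph also plans a direct comparison of steroid use between the arms.

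**The concern.** A term birth cannot satisfy the definition. If the variable is a plain yes/no, the *no* group pools three kinds of birth: all term births, preterm births without steroids, and preterm births with steroids outside the interval. Term births dominate that group and have far better neonatal outcomes for reasons unrelated to steroids. Comparing *yes* with *no* is then mostly a comparison of preterm with term birth, which the listed covariates cannot remove.

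The interaction inherits the problem, because the make-up of the *no* group depends on each group's preterm rate. Section 4 models the treatment effect as a shift in gestational age at birth, and the higher and not-higher-risk groups are formed by a preterm-risk score. The plan therefore expects the compared groups to differ in this respect.

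Section 6.1 names trends in patient care as a possible source of bias. A reader of the steroid results could take them as evidence of steroid harm, or of steroids modifying the strategy's effect, when they reflect preterm status.

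**Working it through.** The SAP gives no figure for the steroid analysis, so there is none to reproduce. As a check on the borrowed NMI rates, a simulated one-sided Fisher test at 0.025 with 1,453 versus 10,000 and 0.036 versus 0.023 to 0.020 has power 0.74 to 0.93, consistent with the 0.7 to 0.9 in section 4.

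**Inputs from SAP section 4**
- Preterm rate: "we estimated a historical preterm birth rate of 9.1" per cent.
- NMI of 3 or more in controls: 0.036.
- Arm sizes: about 1,453 and 10,000. Screen-positive rate: 34%.

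**Assumptions (not in the SAP)**
- f, the share of NMI of 3 or more that occurs in preterm births: 60 to 90%, central 80%.
- s, the share of preterm births with optimally timed steroids: 10 to 40%, central 25%.
- Steroids have no effect, and timing is unrelated to outcome within preterm births.

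**Steroid odds ratio in controls, central case**
- Preterm risk = 0.036 × 0.8 / 0.091 = 0.316. This is also the risk in *yes*.
- Term risk = 0.036 × 0.2 / 0.909 = 0.0079.
- Risk in *no* = (0.091 × 0.75 × 0.316 + 0.909 × 0.0079) / (1 − 0.091 × 0.25) = 0.0295.
- Odds ratio = (0.316/0.684) / (0.0295/0.9705) = 15.2.
- Term share of *no* = 0.909 / (1 − 0.091 × 0.25) = 93.0%.

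| f | s = 10% | s = 40% |
|---|---|---|
| 60% | 8.8 | 10.7 |
| 90% | 16.2 | 22.6 |

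These figures are for NMI dichotomised at 3. The weighted ordinal model in section 5.5 was not simulated.

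**Interaction, prospective versus historical.** Suppose the prospective preterm rate is 7% and nothing else changes. The central odds ratio becomes 18.5, so the ratio of odds ratios is 18.5 / 15.2 = 1.21, with a range of 1.12 to 1.27 over the grid. Other scenarios, over f = 50 to 90% and s = 10 to 40%:
- Same preterm rate, preterm risk and timing share in both groups: exactly 1.00.
- Milder preterm outcomes alone bring NMI of 3 or more down to the SAP's 0.023 to 0.020: 0.14 to 0.77.
- Only the optimally timed share doubles: 1.05 to 2.23.

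**Precision in the 7% scenario.** *Yes* births in the prospective arm number 1,453 × 0.07 × s, about 10 to 41. The standard error of the log interaction is 0.40 to 0.79. In the central case it is 0.485, so a ratio of 1.21 has a 95% interval of about 0.47 to 3.1. The two-sided 5% rejection rate rises only to about 5 to 9%.

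**Interaction, higher versus not-higher risk.** If, for example, 60% of preterm births are in the higher-risk group, the preterm rates are 0.091 × 0.60/0.34 = 16.1% and 0.091 × 0.40/0.66 = 5.5%. With 50 to 75% of preterm births in that group and f = 70 to 90%, the false interaction is 0.20 to 0.67.

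**Preterm birth before 37 weeks as endpoint.** This needs no assumption. Every *yes* birth is an event by definition, so the odds ratio is infinite in each group and the interaction cannot be estimated.

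**After restriction to births before 37 0/7 weeks.** Under the same assumptions, the steroid odds ratio and the interaction ratio are both 1.0.

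**The case against.** **The coding is inferred.** The SAP never says that term births are coded 0. Since the interval is defined only for preterm deliveries, an analyst might treat term births as not applicable. That is possible, but it would be an unwritten rule; a binary item with no exclusion puts term births in *no*. Writing the rule down is most of the fix.

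**Many endpoints are not of this kind.** This stands. The exploratory length-of-stay endpoints and one repeat of NICU admission are already limited to premature neonates and escape the artefact. NNOLOS and NICULOS use the top quantile of stay and gestation uses the bottom quantile. At 9.1% preterm, 1.2 × 9.1% = 10.9%, so that quantile is 10%. The effect there was not quantified. The problem is shown for NMI and applies by the same reasoning to MNM, all-birth NICU admission and the preterm birth rates.

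**A false interaction is not certain.** A reader might infer that the interaction must leave 1, and upwards. The documents do not support that: it stays at 1 when the groups match on preterm rate, severity and timing share, and it can move either way. With so few *yes* births, the 7% scenario would rarely produce a significant result.

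**Steroid care is not left unexamined.** A reader might infer that the plan then cannot compare steroid care between eras at all. It can: the planned comparison of use between arms does not depend on this regression.

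**The remedy has its own weakness.** Restricting to preterm births and adjusting for gestational age both condition on events that the strategy is meant to change. This also stands, and limits the restricted analysis to description.

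**Conclusion.** The point holds for endpoints analysed in all births. As written, the steroid variable there is largely a marker of preterm birth, and the odds ratio for NMI of 3 or more is about 9 to 23 with no steroid effect. That size rests on the assumed shares f and s and on coding term births as *no*; the direction holds across the whole range examined. For preterm birth before 37 weeks the model cannot be estimated, whatever the values of f and s.

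The interaction is distorted conditionally, in a direction that is not fixed, and by an amount that is small beside its standard error in the prospective-versus-historical case worked above. The SAP's own effect model and its risk-group contrast make the condition likely to be met.

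This is one exploratory analysis. It would be too strong to read the defect as touching the co-primary tests, which do not use the steroid variable. No view is taken on the timing interval itself.

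**What to change.** In the corticosteroid paragraph of SAP section 5.7:

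- Restrict the steroid regression and its group interaction to births before 37 0/7 weeks, the population in the variable's own definition.
- Drop preterm birth before 37 weeks as an endpoint for this regression.
- Where numbers allow, separate steroids given outside the interval from steroids not given.
- Report results with and without adjustment for gestational age at birth.
- Present them as descriptive estimates with intervals, and say that the set is selected on a post-treatment event.
- Keep the planned between-arm comparison of steroid use.

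The cost is SAP wording only. The price is precision: at 9.1% preterm the prospective arm supplies about 0.091 × 1,231 = 112 to 0.091 × 1,453 = 132 births. The lower figure removes the 45% of higher-risk subjects assumed not to comply, 1,453 × (1 − 0.34 × 0.45) = 1,231. A three-level variable crossed with group will be sparse in a set of that size.

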5.1 Analysis Populations

One control population will be considered in primary analyses: the historical control population. The historical control population includes all subjects who attended ChristianaCare during the eligibility period and who satisfy all eligibility criteria.

The historical control arm will be the control population for primary and alternative analysis of the primary, secondary and exploratory endpoints.

Seven subject populations will be considered in the analyses: an Intent-to-Treat (ITT) population, a modified ITT population, a completer(s) population, a compliant completers population, a non-intervention completers population and a safety population. The completers, compliant completers, non-intervention completers and modified ITT populations are subsets of the ITT population.

The ITT population includes all historical subjects selected and all prospective patients enrolled regardless of whether or not the co-primary outcomes were observed, or in the prospective arm, any PreTRM test result has been generated or intervention consent has been signed. Subjects with missing outcomes will be handled as described in the missing data sensitivity analyses.

The modified ITT (mITT) population includes all subjects for whom both co-primary outcomes are known; and who have either been selected for the historical control group, received a not-higher-risk PreTRM® test result, or consented to and initiated treatment before 24^{0/7} weeks gestation after receiving a higher risk PreTRM® test result.

The completers population includes subjects for whom both of the co-primary outcomes are known, and, in the prospective arm, for whom a PreTRM® test result was generated.

The compliant completers population includes ITT subjects who have missed no more than 20% of daily doses for both low-dose aspirin and vaginal progesterone, and participated in weekly care management calls with no more than 20% missed weeks.

The non-intervention completers population includes all ITT subjects who received a higher-risk PreTRM® test result but neither consented to nor initiated treatment before 24^{0/7} weeks gestation.

The safety population includes all eligible subjects who gave consent to participate in the study and attempted a blood draw for the PreTRM® test, regardless of receipt of study interventions.

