6.2 Potential differences between historical and prospective cohorts

The assessment of selection bias involves assumptions regarding inclusion or participation by potential subjects, and results can be highly sensitive to assumptions. Even with external validation data, which may work for unmeasured confounders, it is difficult to account for more than a trivial amount of selection bias. Self-selection bias in consenting of higher-risk subjects to interventions further depends on PreTRM® score, a

factor measured only in the prospective arm. Assessment of epoch bias adds assumptions regarding the composition of standard care and incidence of comorbid conditions due to public health trends. Since the study population is a hybrid of prospective cohort and historical cohort, instead of randomized clinical trial, bias is the key issue in the analysis of outcomes. Using appropriate methods to address bias is critical in the study. Different approaches have been applied, including multivariate analysis with covariate adjustment in the studies in which selection bias needs to be handled, and more recently, propensity scoring. Propensity score analysis, includes subgroups defined by propensity score, propensity score used as a covariate in multivariate analysis, matched patients in two groups by propensity score, and inverse probability weighting. Methods based on propensity scores have become important in addressing selection bias in recent years. Other methods are instrumental variable and regression discontinuity design (RDD).

Comparison of diverse adjustment methods as specified in the primary, secondary and exploratory analyses will enable assessment of the degree of selection and epoch bias in the study, and the quality of prespecified and exploratory adjustments for bias.

As well, exploratory analyses within the prospective arm will provide additional estimates of intervention efficacy without reference to historical controls.

Statistical Analysis Plan for AVERT Economic Study (SEAR, Separate Document)

REFERENCES

- 1 Anderson, Robert N, and Betty L Smith. 2003. “Deaths: Leading Causes for 2001.” *National Vital Statistics Reports : From the Centers for Disease Control and Prevention, National Center for Health Statistics, National Vital Statistics System* 52 (9): 1–85. <http://www.ncbi.nlm.nih.gov/pubmed/14626726>.

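### The risk-score discontinuity analysis uses the mITT set, which removes untreated women only at or above the 16% threshold, so a jump there can arise without any treatment effect

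*SAP*

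**What the plan says.** SAP section 5.7 plans an analysis inside the prospective arm, in which endpoints "will be assessed in the prospective portion of the mITT population as dependent responses to nonrandom quantitative assignment of treatment". The PreTRM risk score is the assignment variable. The SAP states the inference in advance: "A discontinuity at the intervention threshold in the relationship between outcome and risk score observed in the prospective arm will demonstrate intervention effect". The effect is then to be "re-assessed as the estimated risk-score dependent difference between compliant completers and non-intervention completers".

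The same paragraph says of this analysis that "it is independent of any selection biases or epoch effects present in comparisons of the prospective arm", and the sentence ends by limiting this to comparisons with historical controls. It then acknowledges that bias may exist within the prospective arm. For that it plans three versions: unadjusted, adjusted for the primary-analysis covariates, and adjusted by the propensity score of the alternative analysis.

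Section 5.1 defines the mITT set. Both co-primary outcomes must be known. A prospective woman then enters if she "received a not-higher-risk PreTRM® test result", or if she "consented to and initiated treatment before 24^{0/7} weeks gestation after receiving a higher risk PreTRM® test result". Section 3.3 sets the threshold at a 16% risk.

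Section 6.2 relies on this family of analyses: "exploratory analyses within the prospective arm will provide additional estimates of intervention efficacy without reference to historical controls".

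**The concern.** A threshold analysis is informative because women just below and just above the cut should be alike except for what the cut triggers. That requires the analysis set to be formed in the same way on both sides. Here it is not. Below the cut the set contains women who would have accepted treatment and women who would have declined it. At or above the cut it contains only those who accepted and started in time. Self-selection switches on at the very score where the analysis looks for a jump.

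The study is not randomised, and the SAP presents within-arm results as a check that does not lean on historical controls. A jump would probably be read as corroborating the main comparison. As written, it could instead reflect who agreed to be treated.

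**Working it through.** The SAP gives no numerical figure for this analysis, so there is none to reproduce.

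**Inputs from the SAP**
- Prospective subjects: about 1,453 (section 4).
- Share at or above the threshold: 34% (section 4).
- Compliance among higher-risk subjects: 55% (section 4). The SAP gives no acceptance rate, so this stands in for acceptance, *a*. Range examined: 40% to 70%.
- NMI ≥ 3 proportion in controls: 0.036; preterm birth rate: 9.1% (section 4). Each is used in turn as the outcome risk at the cut.

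**Assumed, not in the SAP**
- *k*, the ratio of decliners' to acceptors' outcome risk near the threshold without treatment effect. Range examined: 0.75 to 3.

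**Step 1. How many women the rule removes.** At or above the cut: 1,453 × 0.34 ≈ 494. Kept: 494 × 0.55 ≈ 272. Removed: about 222. Below the cut there are about 1,453 × 0.66 ≈ 959, and none is removed for declining.

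**Step 2. The jump with no treatment effect.** Let *r* be the risk of all women at the cut and *p* the acceptors' risk. Then *r* = *a·p* + (1 − *a*)·*k·p*, so *p* = *r* / (*a* + (1 − *a*)*k*). Just below the cut the set shows *r*; just above it shows *p*. The no-effect ratio is 1 / (*a* + (1 − *a*)*k*).

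| *k* | *a* + (1 − *a*)*k* at *a* = 0.55 | Ratio at the cut |
|---|---|---|
| 0.75 | 0.8875 | 1.13 |
| 1 | 1.0000 | 1.00 |
| 1.25 | 1.1125 | 0.90 |
| 1.5 | 1.2250 | 0.82 |
| 2 | 1.4500 | 0.69 |

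At *k* = 2 the ratio is 1/1.6 = 0.63 with 40% acceptance and 1/1.3 = 0.77 with 70%.

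**Step 3. Chance of a false positive.** A simulation with no treatment effect started from 1,453 women. Risk rose smoothly with the rank of the score, and acceptance was 55% regardless of score. A logistic model with a step at the cut and a slope in the score rank was tested one-sided at 5%. The one-sided level is an assumption taken from the SAP's rule for primary and secondary endpoints.

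| *k* | mITT, risk 0.036 | mITT, risk 0.091 | All scored women, risk 0.036 | All scored women, risk 0.091 |
|---|---|---|---|---|
| 1 | 4.9% | 3.5% | 6.1% | 4.7% |
| 1.5 | 9.9% | 11.2% | 6.3% | 3.6% |
| 2 | 14.8% | 24.1% | 5.7% | 3.7% |
| 3 | 24.3% | 45.4% | 6.2% | 4.8% |

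With all scored women kept, the large-sample odds ratio at the cut was 1.01 to 1.02 for every *k*. In the mITT set it was 0.82, 0.69 and 0.52 for *k* = 1.5, 2 and 3.

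**Step 4. Do the planned adjustments help?** The primary covariates in section 5.3 are maternal age, parity and substance use disorder assessed through neonatal opioid withdrawal. The propensity score there models membership of the prospective rather than the historical group. Neither models acceptance among higher-risk women. The ITT, completers and bootstrap replications in section 5.7 repeat the primary and alternative analyses, not this one.

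**Step 5. The re-assessment.** Compliant completers and non-intervention completers are both defined by the women's own behaviour. If compliant completers carry the acceptors' risk, the no-effect ratio is 1/*k*: 0.67 at *k* = 1.5 and 0.50 at *k* = 2. The two sets also leave out higher-risk women who started but fell short of the compliance rule, and those who consented but did not start in time.

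**The case against.** The strongest reply has four parts.

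- **The SAP is more careful than a quick reading suggests.** It claims independence only from biases relative to historical controls, and it plans adjustment for bias inside the prospective arm. That stands, and it would be unfair to say the SAP overlooks within-arm bias. The remedy falls short because none of its adjustments targets acceptance.
- **A false jump is not inevitable.** It needs acceptors and decliners to differ in prognosis near the cut. At *k* = 1 there is none, and below 1 it runs the other way. This stands. The SAP gives no value of *k*, although its abstract and section 6 both treat non-acceptance as a possible source of bias.
- **55% is compliance, not acceptance.** Section 5.1 separates consenting and starting from later adherence. This stands, so the sizes are illustrations over a range. They also describe a binary risk and do not carry over directly to the Cox analyses of length of stay and gestation.
- **The analysis is exploratory.** It lies outside the Holm procedure for the co-primary endpoints. This stands and limits the consequence.

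A reader might also infer two stronger things that the document does not support. One is that section 6.1 declares this particular bias beyond adjustment. That remark gives as its reason the lack of a score-defined higher-risk group among historical controls, so it concerns the historical comparison; within the prospective arm, scores are available for decliners too. The other is that this is the plan's only efficacy estimate free of historical controls. Section 5.7 also compares higher-risk with not-higher-risk women, and compliant with non-intervention completers, within the arm.

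**Conclusion.** The point holds in a conditional form. The mITT rule makes selection change at the threshold, so a discontinuity there cannot by itself demonstrate an intervention effect. It could reflect treatment, differences between acceptors and decliners, or both, and the planned adjustments and re-assessment do not separate them.

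Over an assumed *k* of 0.75 to 2 at 55% acceptance, the no-effect ratio runs from 1.13 to 0.69. The direction depends on whether decliners are at lower or higher risk, which the SAP does not say. The false-positive rates further assume a particular smooth risk gradient and a one-sided 5% test. The co-primary tests are unaffected. What suffers is the value of this analysis as support for them.

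**What to change.** - Run the analysis in the prospective part of the completers population (PreTRM result generated, both co-primary outcomes known), within the same pre-pandemic window. Keep all higher-risk women whatever their uptake.
- Report the discontinuity as the effect of a higher-risk result together with the offer of intervention.
- Replace the statement that a jump will demonstrate effect with wording that gives the assumptions: comparable women either side of the cut and a correctly modelled relation between score and outcome.
- If an uptake-scaled estimate is wanted, use a fuzzy discontinuity, with being at or above the threshold as instrument for starting treatment, in place of the contrast between compliant and non-intervention completers. State that it assumes a higher-risk result affects outcome only through treatment start.

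The cost is a change of SAP wording and modest programming, since the completers population is already defined. The statistical price is larger: the offer effect is diluted by non-uptake and intervals will be wide. At a rate of 0.036, about 494 women above the cut yield 494 × 0.036 ≈ 18 events with NMI ≥ 3, and fewer near the threshold, so a fuzzy estimate for that outcome may be very imprecise. The SAP should say so in advance.
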